## **16.0 Health Information and Privacy Compliance**

*16.1 Select which of the following is applicable to your research:*

- My research does not require access to individual health information.
- I am requesting that all research participants sign a HIPCO approved HIPAA Disclosure Authorization to participate in the research (either the standalone form or the combined consent and HIPAA Authorization).
- I am requesting the IRB to approve a Waiver or an alteration of research participant authorization to participate in the research.

Appropriate Use for Research:

MEDICAL PROTOCOL (HRP-590)

PROTOCOL TITLE: VISUAL SURROUND SUPPRESSION UNDER PSILOCYBIN

VERSION DATE: May 18, 2023

We will only be accessing and retaining records from research participants who have consented to be in the study. We will carefully match the participants information with their appropriate records, and only IRB-approved study staff will have access to these records. If at any time the participant decides to withdraw their consent from the study, all copies of their records will be destroyed in a HIPAA-compliant shredder.

16.2 Identify the source of Private Health Information you will be using for your research (Check all that apply)

- I will use the Informatics Consulting Services (ICS) available through CTSI (also referred to as the University's Information Exchange (IE) or data shelter) to pull records for me
- I will collect information directly from research participants.
- I will use University services to access and retrieve records from the Bone Marrow Transplant (BMPT) database, also known as the HSCT (Hematopoietic Stem Cell Transplant) database.
- I will pull records directly from EPIC.
- Other. Describe:

16.3 Explain how you will ensure that only records of patients who have agreed to have their information used for research will be reviewed. N/A

- I will retrieve record directly from axiUm / MiPACS
- I will receive data from the Center for Medicare/Medicaid Services
- I will receive a limited data set from another institution

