## MEDICAL PROTOCOL (HRP-590)

### PROTOCOL TITLE: VISUAL SURROUND SUPPRESSION UNDER PSILOCYBIN

VERSION DATE: May 18, 2023

sharing with the scientific community and deposition of data into repositories that are required for publishing findings in the scientific literature. Additionally, the supplier of the psilocybin compound, Usona Institute, requires access to de-identified safety data from the study. Because we are not sharing any identifiable information with Usona or OpenNeuro, neither a DUA or BAA is required. We have a signed agreement with Usona for the transfer of the compound in exchange for de-identified safety data.

Specimen blood samples will be processed for analysis and then stored by the Cytokine Reference Lab service. These samples will be stored at -80C for at least 5 years to allow for follow-up tests that may be required, such as if new tests become available, or if manuscript reviewers request additional analyses.

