## **12.0 Withdrawal of Participants**

### *12.1 Withdrawal Circumstances:*

Participants will be withdrawn from the research study if any of the following occur while enrolled: 1) participant meets any exclusionary criteria; 2) participant becomes suicidal with intent and plan; 3) participant engages in other harmful behavior towards themselves or others that requires urgent/emergency medical care; 4) participant experiences intolerable adverse effects from the psilocybin or niacin, including allergic reaction; 5) participant fails to adhere to protocol requirements; and/or 6) participant withdraws consent. Decision to withdraw based on these criteria will be determined at the PI's discretion.

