### *12.2 Withdrawal Procedures:*

## MEDICAL PROTOCOL (HRP-590)

### PROTOCOL TITLE: VISUAL SURROUND SUPPRESSION UNDER PSILOCYBIN

VERSION DATE: May 18, 2023

If a participant withdraws or is withdrawn from the research study, no more data will be collected on them. Previous data collected will be stored and analyzed as planned, unless exclusionary criteria is met. If the participant is withdrawn they will be notified by phone or in-person and any scheduled appointments for the research study will be cancelled.

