## MEDICAL PROTOCOL (HRP-590)

PROTOCOL TITLE: VISUAL SURROUND SUPPRESSION UNDER PSILOCYBIN

VERSION DATE: May 18, 2023

first three participants during the pilot phase to assess any SAE/AE or other issues. We will determine together whether we can move forward with the full study design or if modifications need to be made. For the full study design, the team will meet regularly after each additional 10 participants are enrolled and complete the study protocol throughout the duration of the study. Research staff will prepare a report for the DSMB at least 1 week prior to each scheduled meeting. This report will include a protocol synopsis, study personnel, brief statement of purpose, projected timetable and schedule, study summary including a summary of protocol changes, enrollment/participant status, protocol deviations, and adverse event tables (incidence, severity, listing of serious adverse events, adverse events, and deaths) and anything else pertinent to the study, participant safety or DSMB oversight. Safety information will be collected on Case Report Forms, adverse event and protocol deviation logs, and on memos (memo-to-file) requiring additional explanation and PI signature.

The DSMB, along with FDA and UMN IRB, would determine the need to immediately suspend research based on any individual SAE/AE as well as collective AE/SAE parameters. The DSMB, in addition to the FDA and UMN IRB, will be notified of any SAE immediately. The DSMB will be notified in each annual report of the following: AE log (frequency, severity, corrective treatment, duration, relation to study drug, and serious or not serious of each event by participant ID), AE incidence and severity by body system, and listing SAE/deaths.

See Appendix (G) for the DSMB members and charter.

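### When consent is withdrawn, section 16.1 destroys all of the participant's records while section 12.2 keeps and analyses data already collected, and nothing says which rule governs

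*Combined protocol and SAP*

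**What the plan says.** Section 12.1 gives six circumstances in which a participant is withdrawn. Item 4 is that the "participant experiences intolerable adverse effects from the psilocybin or niacin, including allergic reaction". Item 6 is that the "participant withdraws consent".

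Section 12.2 sets the rule for everyone who leaves, by either route: "If a participant withdraws or is withdrawn from the research study, no more data will be collected on them". It continues: "Previous data collected will be stored and analyzed as planned, unless exclusionary criteria is met". The only exception named is meeting exclusionary criteria.

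Section 16.1, under appropriate use for research, says that whenever someone "decides to withdraw their consent from the study, all copies of their records will be destroyed in a HIPAA-compliant shredder". It names no exception for data already collected, for de-identified data or for adverse events.

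Two other sections depend on the same data. Section 18.2 promises the DSMB tables of adverse-event incidence and severity, and an annual event log keyed to participant ID. Section 6.1 says that the supplier of the psilocybin "requires access to de-identified safety data from the study".

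**The concern.** A coordinator whose participant withdraws consent finds one section telling them to keep the data and another telling them to destroy it. If 16.1 is followed as written, the loss cannot be repaired at the analysis stage, because there is nothing left to impute from or to examine for bias.

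The loss is also unlikely to be random. The protocol foresees acute distress during dosing (13.1) and intolerable adverse effects (12.1 item 4). Some participants who have a difficult session may respond by withdrawing consent. Removing their data would tilt both the drug contrast and the adverse-event summary towards those content to stay.

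**Working it through.** The point rests on a comparison of text, so that comes first. The arithmetic only shows scale.

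**1. Do both rules govern the same event?** Yes. Withdrawal of consent is item 6 in 12.1. Section 12.2 covers participants who withdraw as well as those who are withdrawn. Section 16.1 is triggered by withdrawal of consent at any time.

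**2. Are the instructions opposite?**

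| | Section 12.2 | Section 16.1 |
|---|---|---|
| Trigger | Any withdrawal, including of consent | Withdrawal of consent only |
| Data already held | Stored and analysed | All copies of records destroyed |
| Exception | Exclusionary criteria met | None stated |

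No section ranks one rule above the other.

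**3. Does other text restrict *records* in 16.1 to outside charts?** Not expressly.
- Sections 16.3 and 16.4 mark the review of patient records as not applicable.
- Section 13.1, on privacy risks, uses the word for study data: records labelled with the study identifier and held in a secure database.
- Section 16.11 already provides for shredding paper that contains PHI, so a rule confined to such paper would add little.

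**4. What would literal compliance remove?**
- *Source documents.* Sections 15.4 and 17.1 keep de-identified participant data in a folder, and the monitor in 18.1 reviews folders and source documents.
- *Safety data.* Events not yet reported could not enter the DSMB tables or log (18.2) or the supplier's safety data (6.1). Nor could they be evaluated if the study were terminated for safety (12.3).
- *Outcome data.* Section 15.3 plans a repeated-measures ANOVA and a mixed-effects regression with a random intercept. Someone who finishes both dosing sessions and then withdraws consent would be lost to both. Someone who withdraws between sessions could still contribute baseline and first-session data to the mixed model under 12.2, but nothing under 16.1.

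**5. Effect on an adverse-event rate (illustration).** The documents give no consent-withdrawal rate and no expected event rate, so all inputs except N are assumptions. Let N be the number of participants, e the number with the event, and q the share of those e who withdraw consent and are erased. Then

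retained rate = (e − qe) / (N − qe)

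| True rate | q = 25% | q = 50% | q = 100% |
|---|---|---|---|
| 4/40 = 10% | 3/39 = 7.7% | 2/38 = 5.3% | 0/36 = 0% |
| 8/40 = 20% | 6/38 = 15.8% | 4/36 = 11.1% | 0/32 = 0% |
| 4/46 = 8.7% | 3/45 = 6.7% | 2/44 = 4.5% | 0/42 = 0% |

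The N of 40 is the full study (5.1, 5.3). The N of 46 is the number section 10.1 says is needed for analysis, equal to 40 plus the 6 pilot participants. One participant is 1/40 = 2.5% or 1/46 = 2.2%. Neither N is exactly the number exposed to psilocybin, since a niacin-first participant who leaves before Visit 4 never receives it.

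**6. Effect on power.** Section 15.2 states 92% power with 16 subjects but gives no effect size or standard deviation, so the figure cannot be reproduced. It can only be solved backwards. With a two-sided alpha of 0.05 (sidedness is not stated) and the noncentral t distribution, 92% implies a standardised paired difference of 0.90 with 16 subjects, or a standardised difference of 1.23 with 16 per arm. Holding those effects fixed:

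| Lost of 40 | Remaining | Power, paired | Power, two groups |
|---|---|---|---|
| 0% | 40 | above 99% | 96.6% |
| 5% | 38 | above 99% | 95.8% |
| 10% | 36 | above 99% | 94.8% |
| 20% | 32 | above 99% | 92.0% |
| 30% | 28 | above 99% | 87.9% |

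For a crossover the paired column is the natural one. The harm is selective loss, not loss of sample size.

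**The case against.** The best defence is that *records* in 16.1 means health records obtained about a person. The sentence closes a short paragraph in the health-information section about accessing records and matching them to the right participant. A shredder handles paper, and 16.11 uses the same device for paper with PHI only. Study data sit in REDCap and Box (6.1), and MRI and EEG files are processed on imaging or supercomputing servers (16.7), none of which a shredder reaches. Section 19.2 allows access to medical records with written consent, and the tick-boxes in 16.1 and 16.2 did not survive in the text reviewed, so the source of records cannot be settled. This makes the narrow reading plausible. It does not remove the conflict, because the sentence says all copies and states no such limit.

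Safety data are also better protected than 16.1 alone suggests. Section 18.2 requires immediate notice of serious adverse events to the DSMB, FDA and IRB. It keeps safety information in logs and memos as well as case report forms, and schedules DSMB meetings as participants complete. Destroying a folder does not undo a report already sent. The exposed material is mainly non-serious events not yet reported, source documents and outcome data.

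Three stronger inferences are tempting, and the documents do not support them:
- *That data are erased for everyone who quits after dosing.* Section 16.1 is triggered only by withdrawal of consent. Leaving for intolerable adverse effects or non-adherence falls under 12.2 alone unless consent is also withdrawn.
- *That an adverse-event rate would fall to zero.* That needs every affected person to withdraw consent and every log, file and earlier report to disappear.
- *That the protocol clearly orders outcome data erased.* The wording permits that reading but, given its context, does not settle it.

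**Conclusion.** The contradiction is real. For withdrawal of consent, 12.2 keeps and analyses what 16.1 destroys, and no text reconciles them. On the literal wording of 16.1, a site would irreversibly remove source documents, outcome data and not-yet-reported adverse events for participants who formally withdraw consent, contrary to 18.2 and 6.1.

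The size is unknown, because no consent-withdrawal rate is given. The rates shown are illustrations under assumed inputs. Power is barely affected under the paired reading. Under the two-group reading it falls below 92% only when more than 20% of the 40 are lost.

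The conclusion assumes that *records* carries its unrestricted meaning. If the sponsor intended only paper or identifiable copies of health records, the practical harm is small, but the sentence still needs to say so. The combined consent and HIPAA form may already address this. It was not available for this review, which is not a defect in the plan.

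**What to change.** Rewrite the 16.1 sentence to match 12.2. On withdrawal of consent:

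- no new study data and no outside health information are obtained from that date;
- data collected up to that date, including all adverse events, are retained under the study ID, reported to the DSMB, FDA and supplier as the protocol requires, and analysed;
- destruction is limited to identifiable copies of outside health records that are not needed as source documents.

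Use the same wording in the consent and HIPAA form, so that participants are told what happens to data already collected.

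The cost is one sentence in the protocol and matching form text, with no extra data or staff. The exclusionary-criteria exception in 12.2 is a separate rule, which this change does not address. It also lets data collected after randomisation be dropped, so it should be clarified in the same amendment.

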16.4 Approximate number of records required for review: N/A

16.5 Please describe how you will communicate with research participants during the course of this research. Check all applicable boxes

- This research involves record review only. There will be no communication with research participants.
- Communication with research participants will take place in the course of treatment, through MyChart, or other similar forms of communication used with patients receiving treatment.

## MEDICAL PROTOCOL (HRP-590)

### PROTOCOL TITLE: VISUAL SURROUND SUPPRESSION UNDER PSILOCYBIN

VERSION DATE: May 18, 2023

Communication with research participants will take place outside of treatment settings. If this box is selected, please describe the type of communication and how it will be received by participants.

- We will communicate with participants via telephone (using a study-specific phone number) for pre-screening, appointment scheduling, appointment reminders, etc. We will also communicate through text message or unsecure email if the participant agrees in writing by signing the [GUIDELINES AND CONSENT FOR TEXT MESSAGE CORRESPONDENCE FOR RESEARCH PARTICIPANTS](#) and/or [GUIDELINES AND CONSENT FOR UNSECURED EMAIL CORRESPONDENCE FOR RESEARCH PARTICIPANTS](#).

#### 16.6 Access to participants

The research team will be permitted to access sources of private information because all participants will be required to sign a HIPAA waiver at the time of informed consent.

#### 16.7 Location(s) of storage, sharing and analysis of research data, including any links to research data (check all that apply).

In the data shelter of the [Information Exchange \(IE\)](#)

Store       Analyze       Share

In the Bone Marrow Transplant (BMT) database, also known as the HSCT (Hematopoietic Stem Cell Transplant) Database

Store       Analyze       Share

In REDCap (recap.ahc.umn.edu)

Store       Analyze       Share

In Qualtrics (qualtrics.umn.edu)

Store       Analyze       Share

In OnCore (oncore.umn.edu)

Store       Analyze       Share

In the University's Box Secure Storage (box.umn.edu)

Store       Analyze       Share

In an AHC-IS supported server. Provide folder path, location of server and IT Support Contact:

The path should be in the form of "\vp.ahc.umn.edu\vp\Research\Study0004" HIPCO requires this information to verify the data are in a properly encrypted server.

MEDICAL PROTOCOL (HRP-590)

PROTOCOL TITLE: VISUAL SURROUND SUPPRESSION UNDER PSILOCYBIN

VERSION DATE: May 18, 2023

Store       Analyze       Share

In an AHC-IS supported desktop or laptop. Provide UMN device numbers of all devices where such information will be stored, location(s) of device(s) and IT Support Contact:

AHC-IS supported laptop, device # 20170890, # 20192519, and # 20191654; and AHC-IS supported desktops, device # 20201941 and # 20201942.

Store       Analyze       Share

Other. Blood samples that are collected from participants at the CRU will be labeled with a de-identified subject code and date, and aliquoted by the study staff and stored by the Cytokine Reference Lab (CRL). Samples will be logged using a de-identified label/code for study participants to keep track of their location within the storage boxes housed in the CRL freezer. De-identified samples will be analyzed by the cytokine laboratory. Only approved study staff will have access to identifying information for these samples. Additional data processing and analysis for MRI and EEG data will be done on either the CMRR server, or on the MSI server due to the size and complexity of the data. Additionally, de-identified processed EEG and fMRI data will also be shared in OpenNEURO (openneuro.org). Audio and video recording from Zoom sessions will be stored on the AHC-IS supported laptop temporarily after each study visit, and then transferred to the UMN Box secure storage for the study. Audio and video recordings from video camera collected during in-person dosing sessions will be transferred to the AHC-IS supported laptop temporarily after each session and then transferred to the UMN Box secure storage for the study. A secure, encrypted, AHC-IS supported external hard drive will be used for temporary storage and analysis of video data, due to large file sizes of the videos. Only approved study personnel will have access to the UMN Box folder for this study, and audio/video data will be used to monitor adherence to lab protocols and for education and training purposes for study personnel.

16.8 Consultants. Vendors. Third Parties. None

16.9 Links to identifiable data: Identifying information about research participants will be contained in a password-protected spreadsheet that is stored on AHC-IS approved devices by the approved study team members, as well as backed up in UMN Box. Only approved study staff will have access to identifying information and will only be permitted to access this on approved devices and on UMN Box.

16.10 Sharing of Data with Research Team Members. Data will only be shared with research team members through UMN Box. De-identified EEG and fMRI data will also be deposited into OpenNEURO (openneuro.org).

*16.11 Storage and Disposal of Paper Documents:* Any paper documents will be scanned to PDF and stored in the HIPAA compliant UMN Box. Paper records containing any PHI will be shredded in a HIPAA approved paper shredder/disposal container.

## **17.0 Confidentiality**

### *17.1 Data Security:*

All information and data collected from and about participants during the research study will be de-identified and kept in the participants folder in a locked cabinet in a locked room accessible only by approved research staff. Identifiable forms such as screening forms containing DOB and consent forms will be kept separate from participant data. All research staff and volunteers are required to complete data safety and security and HIPAA training according to University of Minnesota policy. All data electronically stored and transferred will be de-identified and any identifiable pieces of information stored electronically will be kept secure accessible by only research staff and will be encrypted if transferred or using secure portal such as Box or REDCap. We will be applying for a Certificate of Confidentiality (CoC) through the FDA once we have IRB approval.

## **18.0 Provisions to Monitor the Data to Ensure the Safety of Participants**

### *18.1 Data Integrity Monitoring.*

Data integrity monitoring will be conducted at outset, every 6 months, and upon study closing by the Clinical and Translational Science Institute monitor assigned to the Department of Psychiatry and Behavioral Sciences. The monitor will review an on-site regulatory binder as well as participant folders to ensure compliance to the protocol, SOP and other regulatory requirements. The monitor will review consent forms, completion of source documents and case report forms, and appropriate documentation for protocol deviations, personnel changes, staff training, and adverse events, etc. The monitor will have access to and review all necessary documents at a set appointment time. Monitoring reports will indicate enrollment numbers, select changes since the last monitoring visit and any unresolved queries. The research staff will be expected to resolve all queries, and notify monitor of these resolved queries, within 10 days of receiving the monitoring report.

### *18.2 Data Safety Monitoring.*

A Data Safety Monitoring Board will be appointed for this research study. The DSMB will initially meet prior to enrolling the first participant, and then again after we have completed the

## MEDICAL PROTOCOL (HRP-590)

PROTOCOL TITLE: VISUAL SURROUND SUPPRESSION UNDER PSILOCYBIN

VERSION DATE: May 18, 2023

first three participants during the pilot phase to assess any SAE/AE or other issues. We will determine together whether we can move forward with the full study design or if modifications need to be made. For the full study design, the team will meet regularly after each additional 10 participants are enrolled and complete the study protocol throughout the duration of the study. Research staff will prepare a report for the DSMB at least 1 week prior to each scheduled meeting. This report will include a protocol synopsis, study personnel, brief statement of purpose, projected timetable and schedule, study summary including a summary of protocol changes, enrollment/participant status, protocol deviations, and adverse event tables (incidence, severity, listing of serious adverse events, adverse events, and deaths) and anything else pertinent to the study, participant safety or DSMB oversight. Safety information will be collected on Case Report Forms, adverse event and protocol deviation logs, and on memos (memo-to-file) requiring additional explanation and PI signature.

The DSMB, along with FDA and UMN IRB, would determine the need to immediately suspend research based on any individual SAE/AE as well as collective AE/SAE parameters. The DSMB, in addition to the FDA and UMN IRB, will be notified of any SAE immediately. The DSMB will be notified in each annual report of the following: AE log (frequency, severity, corrective treatment, duration, relation to study drug, and serious or not serious of each event by participant ID), AE incidence and severity by body system, and listing SAE/deaths.

See Appendix (G) for the DSMB members and charter.

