## **15.0 Statistical Considerations**

*15.1 Data Analysis Plan:*

For this pilot study, EEG and fMRI data will be analyzed using standard software and toolboxes. EEG data will be processed to eliminate artifacts (e.g., eye movements). EEG signal amplitudes will be analyzed statistically to compare across subject groups and experimental conditions, as with the behavioral data. fMRI data will be analyzed using standard software (e.g. FMRIB Software Library, others) according to standard protocols used previously in psychedelic neuroimaging research (Atasoy et al., 2017; Carhart-Harris et al., 2017b; Deco et al., 2018; Roseman et al., 2018) and human connectome project pipelines used at CMRR. Data will either be analyzed on CMRR secure servers, or on the Minnesota Supercomputing Institute (MSI) servers. Other measures of RMEQ-30, WASI-II, 5D-ASC, EDI, EBI, PANAS, NEO-FFI, HVLT-R, BVMT-R, CSSRS, cytokines, vital signs and diagnostic tests will be analyzed in statistical software programs (e.g. R, SPSS, etc) for significant differences between groups, and assessed for statistically significant relationships with EEG, fMRI and the psychophysics tasks. The team investigators and coordinator will be blinded to condition, however an independent study statistician that will not have any interaction with study participants will perform all blinded data analysis, with unblinded secondary analyses performed by [name], [name] and the study coordinator.

*15.2 Power Analysis:*

Previous work with surround suppression tasks by Co-Investigator (Schallmo et al., 2019) determined the appropriate number of participants with the smallest effect sizes and corresponding standard deviations found that 16 subjects would provide an a priori power of 92% for detecting a significant difference in surround suppression between experimental conditions. Assuming that some drop out may occur, we decided to have 20 participants per drug group (age, sex and baseline clinical variables balanced).

*15.3 Statistical Analysis:*

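### Scheduled full-study DSMB meetings are counted in completers, so participants withdrawn for intolerable adverse effects do not bring the next meeting closer

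*Combined protocol and SAP*

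**What the plan says.** Section 18.2 provides for a DSMB meeting before the first enrolment and another in the pilot, once the study has completed the "first three participants during the pilot phase to assess any SAE/AE or other issues". For the full study, "the team will meet regularly after each additional 10 participants are enrolled and complete the study protocol". That sentence speaks of the team, but it stands in the DSMB section and the next one ties a board report to each meeting: "Research staff will prepare a report for the DSMB at least 1 week prior to each scheduled meeting".

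Section 12.1 lists the grounds for withdrawal, at the PI's discretion. One is that the "participant experiences intolerable adverse effects from the psilocybin or niacin, including allergic reaction". Section 12.2 gives the consequence: "If a participant withdraws or is withdrawn from the research study, no more data will be collected on them", and "any scheduled appointments for the research study will be cancelled".

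Section 18.2 also has routes to the DSMB that do not depend on completion. "The DSMB, in addition to the FDA and UMN IRB, will be notified of any SAE immediately". An annual report gives the board the AE log by participant, with severity and whether each event was serious, plus incidence by body system. The board, with the FDA and the IRB, can suspend the research on a single event or on the accumulated pattern.

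**The concern.** A safety schedule should advance with the number of people exposed. Here it advances with the number who get through the whole schedule. Someone whose participation ends because the study drug was not tolerated is among the most informative cases for a safety board, yet that person does not move the next scheduled meeting nearer. The interval between meetings, measured in people started, therefore lengthens as tolerability worsens, at any enrolment speed.

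At stake is the time until the board sits down to review adverse events that end participation but are not SAEs. Section 13.1 itself notes that a severe event need not be a serious one, so a severe reaction that leads to withdrawal can fall outside the immediate-notification rule.

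**Working it through.** The plan states no figure for the delay, so there is nothing to reproduce. With 40 participants in the full study and no withdrawals, the rule gives one meeting per 10 starters.

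**Inputs**
- Completers per meeting: 10 (18.2).
- Full-study size 40, about 12 weeks per participant, about 3.5 years for the full study, and also a stated pace of 2 participants per week (all 5.3).
- Withdrawal fraction w: not stated. Section 15.2 says only "Assuming that some drop out may occur, we decided to have 20 participants per drug group", after giving 16 as the number that provides the stated power. Reading 16 of 20 as a retention rate gives 1 - 16/20 = 20%. That is an all-cause allowance, not a rate of withdrawal for harm. I use 10% and 20% as illustrations.

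**Step 1: who counts.** Under 12.1 and 12.2 a withdrawn participant has no further visits and no further data, so does not complete. Under 18.2 only completers advance the count.

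**Step 2: starters per meeting.** If each starter completes with probability 1-w, the number of starters needed for 10 completers is negative binomial with mean 10/(1-w).

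| w (assumed) | Mean starters per meeting | 5th to 95th percentile |
|---|---|---|
| 0 | 10/1.0 = 10.0 | 10 |
| 10% | 10/0.9 = 11.1 | 10 to 13 |
| 20% | 10/0.8 = 12.5 | 10 to 16 |

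**Step 3: calendar time to the first full-study meeting.** Approximate it as starters divided by pace, plus 12 weeks. Section 5.3 gives two paces.
- 40 in 3.5 years: 40/(3.5 × 52) = 0.22 per week. With w = 0, 10/0.22 + 12 gives about week 58. With w = 20%, 12.5/0.22 + 12 gives about week 69. The delay is about 11 weeks.
- 2 per week: 10/2 + 12 = week 17 with w = 0, and 12.5/2 + 12 = about week 18 with w = 20%. The delay is about 1 week.

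**Step 4: the same meeting if withdrawn participants count.** The trigger is reached when 10 dosed participants have completed or been withdrawn. That takes 10 dosed participants whatever w is, so the meeting falls no later than the w = 0 case: about week 58 at the slower pace, week 17 at the faster.

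**The case against.** The strongest reply is that the protocol already covers most of the gap. SAEs reach the board at once. Two of the harm-related withdrawal grounds, suicidality with intent and plan and harmful behaviour needing urgent care, may well be reportable as SAEs. The annual report contains the non-serious events and does not wait for completers. At 40 participants in 3.5 years, about 40/3.5 = 11.4 start each year, so that report recurs roughly every 11 starters, close to the meeting interval itself. At the faster pace the delay is only about a week. Appendix G, which may provide for ad hoc meetings or define completion, is not in the documents.

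All of this stands and limits the point. It does not remove it: for non-serious events the only stated routes are the completer-triggered meeting and a report that may come up to a year later, and a report is not a meeting.

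A reader might infer more than the documents support:
- **That harm is hidden from the board.** The AE tables for a meeting are not limited to completers, and 12.2 generally keeps data already collected. The wording affects when the board meets, not what it sees.
- **That the pilot review must wait for three completers.** The text names the first three participants. It can be read as being finished with those three people, so no delay can be calculated for it.
- **That any withdrawal cancels the last of four meetings.** This assumes no replacement, which is not stated; 10.1 says 46 are needed for analysis, which is 6 + 40. A meeting held after all 40 had completed would in any case protect no full-study participant.
- **That the delay is large.** High withdrawal rates have no source in the documents.

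**Conclusion.** The point holds in a limited form. On its plain wording, the full-study trigger in 18.2 leaves out participants withdrawn for intolerable adverse effects, so scheduled meetings slip as withdrawals rise. The size is modest: 11.1 starters per meeting at 10% withdrawal and 12.5 at 20%, instead of 10. At 20%, the first meeting moves by about 11 weeks at the slower stated pace and about 1 week at the faster. These figures rest on an assumed w and on steady enrolment. The affected oversight is the scheduled review of non-serious adverse events that end participation; serious events are not held back. This is a wording weakness in the schedule that is worth correcting because correction is nearly free, not a failure of safety monitoring as a whole.

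**What to change.** Reword the full-study trigger in 18.2 so that the DSMB meets each time a further 10 participants who have received at least one dose have either finished the protocol or been withdrawn. For the pilot, state that the first three dosed participants count whether they finish or are withdrawn. Put the same wording in the DSMB charter.

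Counting simply from the first dose would be weaker. Group B receives niacin first (5.1), so a meeting could then rest partly on people still in the study who have not yet had psilocybin. Counting on final status avoids that for everyone who is not withdrawn before the second session.

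The cost is one sentence in 18.2 and one in the charter. No extra data are needed, and no dose or clinical rule changes. Meetings fall slightly earlier than under the present wording whenever someone is withdrawn, with correspondingly fewer completers at each.
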